15.4	PERSONAL DATA PROTECTION	19
16	REFERENCES	20

APPENDICES

- I Declaration of Helsinki**
- II Patient Information Sheet and Informed Consent**
- III Investigator agreement**
- IV Accolade Component Sizes**
- V Trident Component Sizes**
- VI Tritanium Component Sizes**
- VII X3 Component Sizes**
- VIII Head Component Sizes**
- IX Accolade II Component Sizes**

THE ATX REGISTRY

ACCOLADE/ACCOLADE II STEM & TRIDENT/TRITANIUM CUP WITH X3 INSERT

INTERNATIONAL MULTICENTRE SURVEILLANCE REGISTER

PROTOCOL SUMMARY

- **Surveillance design:**

International multicentre, prospective follow-up of a consecutive series of patients.

- **Objectives:**

To verify the Accolade/Accolade II stem and Trident/Titanium cup safety during follow-up and survivorship as described by Kaplan-Meier survival curves.

To document the patient clinical outcome of the patients who are eligible for a hip arthroplasty surgery involving an Accolade/Accolade II stem and Trident/Titanium cup.

- **Regulatory status of the device:**

Name of the hip system: Accolade™ TMZF® hip stem. Accolade II stem. Trident and Titanium cup and X3-liner. All components are CE-marked and approved for sale in Europe.

- **Participating institutions:**

Each clinic need to recruit at least 20 patients and maximum 100 patients. Institutions willing to participate to the register and fulfilling the local and international applicable regulatory requirements can participate. Sufficient human and technical resources in the centre are expected to ensure optimal data collection.

- **Patients to be enrolled:**

All patients eligible for a hip arthroplasty surgery involving the Accolade or Accolade II stem and Trident or Titanium cup who have been informed about this surveillance register and who freely consent to participate will be enrolled in the register.

Patients will be enrolled prospectively.

- **Clinical evaluations:**

Adverse events/adverse events: All intra-operative and post-operative adverse events.

Standard clinical parameters, Harris Hip Score, Oxford Hip Score and EQ5D will be registered preoperatively and at each follow-up visit.

ATX-REGISTRY

INTERNATIONAL MULTICENTRE SURVEILLANCE REGISTER

1 INTRODUCTION

Total hip replacement is one of the most common and successful techniques used in orthopaedic surgery. Alongside with cemented hip arthroplasties, cementless hip replacement has proven its value [1-6]. Still, the survival of hip implants is not indefinite. One of the causes for implant failure is loosening and osteolysis as a consequence of particulate wear or stress-shielding.

Many studies have investigated the factors that influence implant fixation and stability [7, 8]. Over the years knowledge on stability, fixation and preservation of bone stock has increased considerably. Also better understanding of joint kinematics allows designing implants with reduced joint reaction forces which again may lead to improved survival of implants. Stem designs have been changed accordingly. Important features in stem design are fit and fill, stem geometry, strain distribution, type and extent of coating [7-11]

Tapered stems, designed to provide mediolateral stability within the femoral canal, have had greater success. A clinical register in which 71 cases were implanted with a wedge fit, cobalt-chrome, cementless stem, resulted in a revision rate of 0% for aseptic loosening, and incidence of thigh pain of 1.4% at a minimum ten year follow-up.¹² This is lower than incidence of thigh pain at earlier visits, where it is reported to be 5% at two years follow-up. Decrease in thigh pain is seen with continuing follow-up. In a register conducted by Pellegrini et. al.¹³ a 3.5% rate of thigh pain was reported at a mean follow-up 6.5 years (range five to eight years). Likewise, lower rates of thigh pain have been reported with similar tapered wedge fit designs: 4% by Hozack et al¹⁴ and 6% by McLaughlin and Lee.¹⁵ Conversely, higher rates of thigh pain have been reported with some uncemented femoral stems with different designs. Rates of thigh pain for different stem designs have been reported to be 9.4% by Engh and Massin¹⁰, 15% by Heekin et al¹⁷ and 20% by Maloney et al¹⁸. The superior results seen with the wedge fit stem can be partially attributed to excellent initial stability with subsequent bone in-growth.¹² It is likely that the tapered design allows for gradual transfer of stresses from the stem to the bone. Engineering analysis of the tapered design has been published which supports the stress transfer effect.^{12, 13, 19}

The Stryker Accolade™ Femoral Component is a relatively new hip system constructed from a beta titanium alloy (TMZF®). The alloy can, which can offer 25% greater flexibility than standard Ti-6Al-4V, yielding a modulus that more closely approximates that of bone. In addition, this proprietary alloy maintains a 20% higher tensile strength than Ti-6Al-4V. Other features include a circumferential plasma spray over the proximal body that assists with mechanical engagement in bone and provides an optimum interface for fixation. Fixation is aided by a HA coating. (2 Pure Fix™) which is 50µm thick and has good mid to long term clinical results (10 years) in a multi-centre register.

Accolade II is the first Morphometric Wedge design, an evolution of the tapered wedge stem. The stem is uniquely designed with a size specific medial curvature to fit a broad range of bone sizes and shapes found in today's patient population (*Optimized length and fit based on a sample size of 556 CT scans*).^{22,23} Mechanical testing has shown this design facilitates initial press-fit stability²⁴ and load transmission in the proximal region of the femur.

The tapered wedge design of the Accolade TMZF and Accolade II Femoral Component provides firm mediolateral stability within the femoral canal. An offering of standard (132°) and extended (127°) offset options enhances soft tissue tensioning without significantly affecting leg length when adjusting joint stability. Furthermore, the TMZF alloy provides the opportunity to reduce the neck geometry thus optimizing the available range of motion while maintaining strength. The system is also designed for use with the V40™ femoral head with the associated range of offsets and neck lengths. Both forged Vitallium® alloy and zirconia ceramic heads can be used.

The aim of this register is to determine the Accolade/Accolade II stem and Trident/Titanium cup survivorship over years.

2 SURVEILLANCE DESIGN

This is a prospective international multicentre surveillance register. The surveillance register will be conducted in accordance to the applicable regulatory requirements including local health data protection laws. Where applicable, Ethics Committees will be informed about the register and if required, Ethics Committee authorisation/favourable opinion will be asked prior to the register start.

All institutions willing to participate to the register, able to recruit at least 20 patients (up to 100 patients) and fulfilling the local and international applicable regulatory requirements can participate. Sufficient human and technical resources are expected in the institution to ensure optimal data collection. All patients eligible for a hip arthroplasty surgery involving the Accolade or Accolade II stem and Trident/Titanium cup who have been informed about this surveillance register and who freely consent to participate will be enrolled in the register (written informed consent described in appendix 3 will be obtained from the patients).

3 OBJECTIVES & METHODS

- Safety & survivorship: All adverse events / failures or revision of the Accolade stem, Accolade II stem and Trident/Titanium cup will be documented in order to draw Kaplan Meier survival curves of the Accolade stem and Trident/Titanium cup over follow-up.
- Clinical outcome: Standard clinical parameters (Harris hip score, Oxford Hip Score and EQ5D) will be obtained to allow the surgeon to assess the clinical outcome of the patient.

The register will follow the standard clinical procedures used by the institutions for patient selection for hip arthroplasty surgery, patient surgery and patient follow-up. Therefore there will be, with regard to this register, no additional assessment, examination, procedure or follow-up visits compared to those usually performed in the institution (routine standard normal procedures).

4 SELECTION OF PATIENTS

4.1 Number of patients

Up to 1000 patients who received the Accolade or Accolade II stem and Trident/Titanium cup with X3 liner can be enrolled into the ATX Surveillance Register.

4.2 Patient selection criteria

All patients in a participating centre matching all of the inclusion criteria and none of the exclusion criteria and who receive the Accolade or Accolade II stem and Trident/Titanium cup with X3 liner will be recorded in the Register.

4.2.1 Inclusion criteria

Patients suitable for inclusion in the trial will be those fulfilling all the following selection criteria:

1. Male and non-pregnant female patients between 18-75 years of age.
2. Patients requiring uncemented primary THA, suitable for the use of the Accolade stem and Trident/Titanium cup.
3. Patients with a diagnosis of osteoarthritis (OA).
4. Patients who understand the conditions of the study and are willing and able to comply with the post-operative scheduled clinical and radiographic evaluations and the prescribed rehabilitation.
5. Patients who signed the Ethics Committee approved Informed Consent Form prior to surgery.

4.2.2 Exclusion criteria

Patients with any of the following will be excluded from the trial:

1. Patients who require revision of a previously implanted hip prosthesis.
2. Patients who had a THA on contralateral side within the last 6 months.
3. Patients who had a THA on contralateral side more than 6 months ago and the rehabilitation period outcome was considered unsatisfactory or not good (Harris Hip Score < 85).
4. Patients who will need lower limb joint replacement for another joint within one year.
5. Patients requiring bilateral hip replacement.
6. Patients who have had a prior procedure of acetabular osteotomy.
7. Patients with acute femoral fractures
8. Obese patients where obesity is severe enough to affect subject's ability to perform activities of daily living (body mass index, kg/m²: BMI ≥ 35).
9. Patients with active or suspected infection.
10. Patients with malignancy – active malignancy.
11. Patients with severe osteoporosis, rheumatoid arthritis (RA), Paget's disease or renal osteodystrophy.
12. Patients immunologically suppressed, or receiving steroids in excess of physiologic dose requirements.
13. The patient has a neuromuscular or neurosensory deficit which would limit the ability to assess the performance of the device or the patient has a neurological deficit which

interferes with the patient's ability to limit weight bearing or places an extreme load on the implant during the healing period.

14. Female patients planning a pregnancy during the course of the study.
15. Patients with systemic or metabolic disorders leading to progressive bone deterioration.
16. Patients, who as judged by the surgeon, are mentally incompetent or are unlikely to be compliant with the prescribed post-operative routine and follow-up evaluation schedule.
17. Patients with other severe concurrent joint involvements, which can affect their outcome.
18. Patients with other concurrent illnesses, which are likely to affect their outcome such as sickle cell anaemia, systemic lupus erythematosus or renal disease requiring dialysis.
19. Patient with a known sensitivity to device materials.
20. Patients under the protection of law (e.g. guardianship).

The patient will be informed by the Investigator (or his designated representative) of the purpose of the data collection. The patient will be informed that his/her medical records are subjected to review as necessary. The confidentiality of the patient will be maintained at all times and the collected data will be anonymous. The patient will be told that he/she is free to refuse the collection of his/her clinical data and to withdraw from the Surveillance at any time without compromising future medical care. A signed Patient Informed Consent will be obtained prior to patient participation (appendix 3).

5 LENGTH OF SURVEILLANCE AND VISIT SCHEDULE

The length of surveillance and patient visit schedule is based on the routine procedures of the institution. The surveillance system is set-up to record data at 1 year, 3 years, 5 years, 7 years and 10 years follow-up.

Visit schedule

VISIT	TIME WINDOW
Pre-op.	Date of or any time post the date of written informed consent up to 4 months prior to the date of surgery.
Operation	N/A
1 year post-op.	± 3 months
3 years post-op.	± 6 months
5 years post-op.	± 6 months
7 year post-op	± 6 months
10 years post-op.	± 6 months

6 DESCRIPTION OF THE DEVICES

[figure not shown]
All components of the THA systems used in this Surveillance obtained the CE mark and are approved for sale and use throughout Europe.

6.1 Femoral Components

The Stryker Accolade™ TMZF® and Accolade II femoral stems are designed for the cementless total hip arthroplasty.

The Accolade® TMZF® is a single use stem intended for cementless fixation, to replace the proximal portion of the femur in primary total hip arthroplasty. The Accolade® TMZF® is a tapered wedge design, comprised of a proprietary beta titanium alloy. The proximal body is plasma sprayed providing an optimum interface for application of Pure Fix™ HA coating. The bone sparing design accommodates either a small or standard size incision or a variety of approaches. There are two neck angles available, the standard 132° and the extended 127°. There are 13 stem sizes available, 9 full sizes (0-8) and 4 half sizes (2.5, 3.5, 4.5, 5.5), for each neck angle. The additional half sizes were developed to accommodate differences in patient anatomy. (See Appendix IV for the device description details).

The Accolade II stem is a morphometric taper wedge design with a size specific medial curvature (see illustration below).

The following table shows the comparison between the Accolade and Accolade II designs and main features:

	Accolade	Accolade II
Medial curvature	• Constant	• Variable
Stem Length	• 110 -146	• 92 -125
Neck finish	• Satin	• Polished
Material	• TMZF	• Ti6Al4V
Tapered design	• 6° A/P Taper • 3° M/L Taper	• 6° A/P Taper • 3° M/L Taper
Coating	• Ti Plasma Spray • PureFix HA	• Ti Plasma Spray • PureFix HA
Neck Angle	• 127 & 132	• 127 & 132
Neck Lengths	• 30, 35, 37, 40	• 27, 30, 35, 37, 40

There are 12 stem sizes for Accolade II (size 0 to 11) for each neck angle. (Please refer to Appendix IX for more Accolade II detailed information)

6.2 Acetabular Component

As Acetabular component either Trident or Trident Tritanium can be used.

Trident®

The Trident™ family of products provides a range of acetabular shells to help surgeons choose the right shell and bearing option for the patient in question. These include PSL or Hemispherical, HA (PureFix™ HA) or non HA coated cups and no hole, cluster hole or multi hole options.

The Trident™ Hemispherical shells are available in sizes 42mm-70mm. The Trident™ PSL shells are available in sizes 40mm-68mm. They can be used with:

- X3™ polyethylene inserts 0°, 10°, excentric, elevated rim, or constrained, in sizes 22mm-44mm (depending on type of insert), for use with either a CoCr, LFIT™ CoCr, Alumina
- Ceramic, BIOLOX *delta* Ceramic, or Orthinox™ head and Alumina inserts 0° in sizes 28mm-36mm, for use with either a Alumina Ceramic or BIOLOX *delta* Ceramic head.
Please note, in this surveillance registry ONLY X3 liner is approved!

TridentTritanium™

TridentTritanium™Acetabular System provides surgeons with a highly porous ingrowth surface.

TridentTritanium™Acetabular System hemispherical shells are manufactured from Commercially Pure Titanium. The TridentTritanium™ shells utilize the screw hole pattern and locking mechanism from the TridentAcetabular system. TridentTritanium™ Hemispherical comes as solid back shells (no holes), cluster shells and multi-hole shells.

The hemispherical shells are available in sizes 44mm-72mm to be used with X3™ polyethylene inserts 0° (in sizes 22mm-44mm), 10° (in sizes 22mm-36mm) or with elevated rim (in sizes 28mm-36mm). The inserts are provided for either a CoCr, LFIT™ CoCr, Alumina Ceramic, BIOLOX *delta* Ceramic, or Orthinox™ heads. **Please note that in this surveillance registry ONLY X3 liners are approved!**

7 PATIENT EVALUATIONS

Patients will be assessed pre-operatively, per-operatively and post-operatively. The follow-up intervals will be as specified in section 5.

7.1 Evaluations at each assessment

7.1.1 Pre-operative Evaluation

- Clinical History

- Patient ID (Study,Site,Subject)
- Date of birth, weight height, Gender
- Visit Date
- Cigarette and Alcohol use
- Charnley patient category
- Previous surgery to hip planned for operation
- Primary Diagnosis

- Clinical Evaluation

- Patient ID (Study,Site,Subject)
- Operative site
- Date of informed consent signed
- Inclusion/ Exclusion
- Harris Hip Score Evaluation
- Oxford Hip Score
- EQ5D

7.1.2 Intra-operative Evaluation

- Surgical details

- Surgery Date
- Operative Side
- Surgical approach
- Minimally invasive surgery and size of incision
- Anaesthesia class and type
- Duration of surgery
- Intra-operative adverse events
- Components used and sizes
 - Solid back / Cluster shells and Multi-hole shells
- Systemic antibiotic prophylaxis
- NSAIDs

7.1.3 Post-operative Evaluation

Patients will be assessed post operatively as per the visit schedule in section 5.

- Clinical Evaluation

- Date of assessment
- Adverse events
- Harris Hip Score Evaluation
- Oxford Hip Score
- EQ5D

7.1.4 Adverse events and device removal events

- Onset date
- When Did the event occur (Intra-op, Post-op)
- Operative site events
- Systemic events
- Device related
- Seriousness
- Treatment
 - Revision/Removal
 - Reoperations
 - Other treatment
- Resolution of event

7.1.5 Termination

- Date of termination of Surveillance
- Date of last visit assessment
- Reason for termination

8 ADVERSE EVENTS

The investigator is required to document all operative site and general medical adverse events, including date of occurrence, date diagnosed, type of complication and treatment.

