8.1 Definitions

8.1.1 Adverse event

An **adverse event** is “any unfavourable and unintended sign, symptom or illness that develops or worsens during the period of observation in the Register. This definition does not imply that there is a relationship between the adverse event and the device under investigation.” [21]

Surgical procedures themselves are not adverse events; they are therapeutic measures for conditions that require surgery. The condition for which the surgery is required is an adverse event, if it occurs or is detected during the Register follow-up period.

A **serious adverse event** is an adverse event which

- a) led to a death
- b) led to a serious deterioration in the health of a subject that
 1. resulted in a life-threatening illness or injury
 2. resulted in a permanent impairment of a body structure or a body function
 3. required in-patient hospitalization or prolongation of existing hospitalisation
 4. resulted in medical or surgical intervention to prevent permanent impairment to body structure or a body function
- c) led to foetal distress, foetal death or a congenital abnormality or birth defect

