12.1 Statistical Analysis

The main aim of the register is to document the patient's safety and survivorship of the Accolade stem and Trident/Titanium cup during the follow-up. The main failure item to be considered for Kaplan-Meier survival curves is surgical revision of the Accolade stem or Trident/Titanium cup but all other adverse events types can be separately considered as failures for Kaplan-Meier survival curve assessment.

In addition to the Kaplan Meier survival curves, the surgeons involved in the register will have the possibility to analyse the following statistical descriptions/comparisons:

- Demographic and pre-operative assessments
- Intra-operative assessments
- Post-operative pain and function assessments: Harris Hip Score
- Oxford Hip Score
- Quality of Life assessments: EQ5D
- Adverse events and device-related adverse events
- Revisions/removals

Frequency and percent distributions will be presented in tabular form for categorical variables. The mean, standard deviation, minimum and maximum values will be presented for quantitative variables.

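### Do the event fields and the failure definition leave the main Kaplan-Meier curve without a revision date, a revised component, or a rule for isolated insert or head exchange?

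*Combined protocol and SAP*

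**What the plan says.** Section 12.1 sets the main analysis: "The main failure item to be considered for Kaplan-Meier survival curves is surgical revision of the Accolade stem or Trident/Titanium cup". Other adverse event types may be treated as failures in separate curves. Section 3 gives the matching data requirement: "All adverse events / failures or revision of the Accolade stem, Accolade II stem and Trident/Titanium cup will be documented", and states that the purpose is to draw the Kaplan-Meier curves.

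The event fields are in Section 7.1.4, headed "Adverse events and device removal events". They include an onset date and a treatment item, under which revision or removal is listed separately from "Reoperations". Section 8 adds "including date of occurrence, date diagnosed, type of complication and treatment". Section 8.1.1 explains: "Surgical procedures themselves are not adverse events; they are therapeutic measures for conditions that require surgery".

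"Components used and sizes" and the surgery date are listed in Section 7.1.2, which covers the index operation. The register's title reads "ACCOLADE/ACCOLADE II STEM & TRIDENT/TRITANIUM CUP WITH X3 INSERT", so the insert is part of the system under surveillance although the failure definition does not name it.

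**The concern.** A revision curve needs an event time, the component revised, and a rule for what counts as failure. On the listed fields, each looks uncertain.

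- **Date.** If surgery is not itself an adverse event, then onset, occurrence and diagnosis dates belong to the condition that led to surgery. A site that enters condition onset puts the failure too early. A site that reads onset as the removal date does not. The two would be mixed in one curve.
- **Component.** Failure is defined by component, but no listed event field records which component was revised.
- **Event.** An isolated insert or head exchange could be entered as a revision or as a reoperation, since neither term is defined. Counting exchanges that are not meant to count makes survivorship look worse. Missing ones that are meant to count makes it look better. This does not fade with longer follow-up or more patients.

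Survivorship is the main aim of the register, so an ambiguous failure definition deserves a check.

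**Working it through.** There is no figure in the plan to reproduce: Section 4.1 gives a cap of 1000 patients, with no expected revision rate or precision target. The check is therefore textual, followed by an illustration on assumed values.

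**Text**

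1. *Date.* The heading of 7.1.4 covers device removal events as well as adverse events. For a removal event, the onset date can be read as the removal date. The statement in 8.1.1 concerns adverse events. Section 12.1 also lists revisions and removals as an output apart from adverse events, which suggests a distinct data item.
2. *Component.* Section 3 requires revisions of the stems and the cup to be documented for the curves, so the component is implied there even though 7.1.4 does not list it.
3. *Event.* Section 12.1 names stem or cup. The Protocol Summary's device list names the liner separately from the cup, Sections 4.1 and 4.2 describe a cup with an X3 liner, and heads have their own Appendix VIII. Read literally, an isolated head exchange is not a failure, and an isolated insert exchange probably is not. What remains open is whether *cup* was meant to include the insert.
4. *Other sources.* A revision normally involves hospital admission and so meets the serious-event definition in 8.1.1. Section 8.2 then calls for a report within 24 hours and detailed written follow-up reports. Section 11 gives access to source records.

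**Size of a dating error**

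Assume 5% revised at 10 years, a constant hazard, and 1000 patients all followed. Then λ = −ln(0.95)/10 and F(t) = 1 − exp(−λt), so F(5) = 2.53%. If a share q of revisions is dated at onset, L years early, the 5-year reading is q·F(5+L) + (1−q)·F(5).

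| Lag L | q = 0.5 | q = 1 |
|---|---|---|
| 3 months | 2.59% | 2.66% |
| 6 months | 2.66% | 2.78% |
| 12 months | 2.78% | 3.03% |
| 24 months | 3.03% | 3.53% |

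The shift is 0.06 to 0.50 points at q = 0.5. At q = 1 it is 0.12 to 0.99 points. The 95% half-width at 5 years is 1.96·√(0.0253·0.9747/1000) = 0.97 points. With 3% or 8% revised at 10 years, the shift at q = 0.5 is 0.04 to 0.30 or 0.10 to 0.79 points.

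At 10 years the shift is zero if follow-up closes then, because every recorded operation counts whichever date is used. If it closes at the late edge of the ±6-month window in Section 5, the shift is at most F(10.5) − F(10) = 5.24% − 5.00% = 0.24 points.

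**Size of the exchange question**

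If a share s of all revision operations are isolated exchanges, leaving them out changes the 10-year figure by F(10)·s. The half-width is 1.96·√(F(1−F)/1000).

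| 10-year revision | s = 10% | s = 20% | s = 30% | Half-width |
|---|---|---|---|---|
| 3% | 0.3 | 0.6 | 0.9 | 1.06 |
| 5% | 0.5 | 1.0 | 1.5 | 1.35 |
| 8% | 0.8 | 1.6 | 2.4 | 1.68 |

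All entries after the first column header are in percentage points. The shift exceeds the half-width only at s = 30% with 5% or 8% revised. At 5% revised, the cases to sort number 1000·0.05·s = 5, 10 or 15.

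**The case for a change.** The strongest reply is that none of the rescue routes is guaranteed. Section 10 says the CRF records the assessments already described, and that is the list lacking these items. The content of the follow-up reports is not specified, and Section 11 says only that monitors may visit. A CRF field for component would still not say whether an insert exchange counts. A definitional difference also does not shrink with sample size, so comparing it with a sampling half-width flatters it.

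Part of this stands. The text does not name these items, and the meaning of *cup* is open to two readings. But Section 7.1 reads as a list of data headings rather than a CRF specification, and the CRF itself is not among the documents, so it cannot be concluded that the items are uncollected. The uncertainty about visits does not limit the right of access to records. The exchange effect rests wholly on assumed shares, and the few cases involved could be resolved by site query. No threshold, comparator or hypothesis test depends on the curve.

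**Conclusion.** No change to the plan is called for. The omission is a gap in detail that an analyst would fill in the ordinary way: time from index surgery to the revision operation, failure as revision of the stem or cup as written, and any isolated exchanges reported separately, as the optional curves in 12.1 allow. The listed fields already support an approximate any-revision curve, which largely serves the main analysis.

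On the assumed values, the dating effect at 5 years makes survivorship look worse, not better, and stays below sampling error unless nearly all revisions are misdated by about two years. It is gone, or nearly so, at 10 years. The exchange question is the weightier part and could reach 2.4 points in the most extreme case examined (8% revised, 30% exchanges). It matters beyond sampling error only at shares that the documents give no reason to assume.

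This conclusion rests on revisions being reported as Section 3 requires, and on the component being obtainable from the CRF, the serious-event reports or the sites. The half-widths assume the full 1000 patients with complete follow-up. A smaller register would be less precise: with 500 patients and 5% revised, 1.96·√(0.0475/500) = 1.91 points, which is above even the 30% exchange case.
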